### Study design:

This is a collaborative study developed by different health and research institutions. The group is composed by BCNatal (Barcelona Center for Maternal Fetal and Neonatal Medicine, *Hospital Sant Joan de Déu*), *Grupo de investigación Infancia y Entorno* (GRIE), Psychiatry Service of *Hospital Clínic de Barcelona* and the Health Department of Catalunya and ASSIR (*Centre d'Atenció a la Salut Sexual i Reproductiva*) of Baix Llobregat.

This is a cluster randomized simple masking controlled trial evaluating the effectiveness of repeated motivational interview (MI) during pregnancy on prevalence of ethanol intake, together with its effects on offspring neurodevelopment.

Data will be collected by the study-site manager and stored in an electronic data-capture database. The coordinator of the study and the statistician will witness the accuracy of the data at the beginning, middle, and end of the study (on-site audit). Data will be captured in a paper form basis and then captured into the electronic database.

### Participants

Inclusion criteria: Maternal age at recruitment at least 18 years old, speak Spanish fluently, women controlling their pregnancy in Baix Llobregat Center, who will attend their delivery in Hospital Sant Joan de Déu and Parc Sanitari Sant Joan de Déu, viable singleton and non-malformed fetus, coursing first trimester of gestation.

Exclusion criteria: Women not willing to participate in the study, multiple gestations, perinatal infections, fetal anomalies including chromosomal abnormalities or structural malformations detected by ultrasound, uncontrolled or/and severe maternal chronic disease, language barriers, impossibility to obtain the sample (hair length shorter than 9 centimeters and/or discolored hair), and premature rupture of membranes.

### Interventions and procedures

For the experimental group, the intervention consists in a MI program during prenatal care visits. MI will be received at least one time each trimester of pregnancy.

For the control group, usual prenatal care attention will be given, but they will be directly asked sign a consent form.

### Intervention: Motivational interview

The MI is integrated in a structure theoretical mark. This method is a person-centered counseling style that increases the intrinsic motivation of the patient to behavioral changes through spirit, acceptance, compassion and evocation. Furthermore, it is a low-cost methodology, and any professional or individual could have been capacitated. Since the motivational interview is a good cost benefit intervention, it is a potential and suitable tool to implement in a healthcare public program.

Professionals whose attend prenatal care visits at centers allocated to give MI will receive previous capacitation (15 hours) dictated by a multidisciplinary expert group who are dedicated several years to MI training and addiction disabilities. This training group is composed by a psychiatrist and a psychologist from *Addictions Unit of Psychiatry Department of Clínic Hospital of Barcelona*

#### Prenatal procedures:

All participants will be followed-up during the pregnancy applying following procedures:

- Questionnaires to evaluate sociodemographic, health and habits background. This questionnaire will be answered during the first trimester of pregnancy.
- SCL-90 (Symptom Checklist): In order to evaluate mental health. This questionnaire will be filled during the first trimester of pregnancy.
- AUDIT-C (Assessment of the Alcohol use disorders identification test): To evaluate ethanol intake. This questionnaire will be filled during first trimester of pregnancy and also up to 7 days after delivery.
- Fetal neurosonography: To evaluate fetal neurodevelopment and brain structure at 28 and 32 weeks of gestation through transabdominal and transvaginal exploration using a General Electric Voluson E10 sonograph (GE Medical Systems, Zipf, Austria).
- Biological samples: Samples will be collected at the moment of delivery to obtain to different biomarkers :
  - o Ethylglucuronide (EtG) on mother's hair: In order to evaluate chronic ethanol intake.
  - o Phosphatidylethanol (PEtH) on dried cordblood spot: In order to evaluate ethanol intake during last 3 weeks prior delivery.

#### Postnatal procedures:

After both groups (the experimental and control) have delivery, a postnatal follow-up to participants (mothers and children) will be given:

- Edinburgh postnatal depression scale (EPDS): This scale evaluates the presence of post-natal depression or anxiety. This questionnaire will be performed to mothers at 6 months from delivery.
- ASQ-3 (Ages and Stages Questionnaires): This parent-report questionnaire could be applied since first month until 5 years and a half of life. It includes 30 questions organized in 5 areas of develop (communication, gross motor, fine motor, problems-solving and adaptative skills). It will apply at 6 and 12 months of age.
- Infant Behavior Questionnaire Revised (IBQ-R): This questionnaire is a parent-report measure of infant temperament. It will be performed at 12 months from delivery.
- Bayley- III test: This test evaluate mental and motor development and also children behavior between 1 month to 42 months of age. It will be performed at 18 months of age.
- Canadian Guidelines for Diagnosis of FASD: It will be evaluated by a pediatrician at 18 months of age regarding the diagnostic criteria of FAS and FASD of Canadian Guidelines.

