### Outcomes

The primary outcome of the study is to demonstrate the effectiveness of repetitive MI to reduce alcohol intake. This will be measured by the presence of ethanol intake biomarkers (EtG in mother's hair and Peth in cordblood).

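### Offspring neurodevelopment is a stated aim measured with five instruments, but no endpoint is named for it, so any of 7 to 17 unranked comparisons could supply the answer

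*Combined protocol and SAP*

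**What the plan says.** Study design gives the trial two objects: the effect of repeated motivational interviewing on alcohol intake, "together with its effects on offspring neurodevelopment". Outcomes covers only the first: "The primary outcome of the study is to demonstrate the effectiveness of repetitive MI to reduce alcohol intake", and "This will be measured by the presence of ethanol intake biomarkers (EtG in mother's hair and Peth in cordblood". It lists no offspring measure, primary or secondary.

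The offspring measures appear only as procedures:

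- Prenatal procedures: fetal neurosonography at 28 and 32 weeks.
- Postnatal procedures, ASQ-3: "It includes 30 questions organized in 5 areas of develop (communication, gross motor, fine motor, problems-solving and adaptative skills". On timing: "It will apply at 6 and 12 months of age". It is described as parent-report.
- Postnatal procedures, IBQ-R at 12 months: "This questionnaire is a parent-report measure of infant temperament".
- Postnatal procedures, Bayley-III, covering mental development, motor development and behaviour: "It will be performed at 18 months of age".
- Postnatal procedures, a paediatrician's assessment against the Canadian FASD guidelines, also at 18 months.

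Statistical analysis gives t, Mann-Whitney, chi-squared and Fisher tests for comparing the groups, by type of variable. It does not say which offspring result leads, how sub-scales are combined, or how several tests are to be handled.

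**The concern.** An aim with five instruments, five ages and no lead measure has no pre-specified answer. If the plan is followed as written, one nominally significant ASQ-3 area at one age could be presented as an effect on neurodevelopment, and a flat Bayley-III result would not count against it. Equally, a real effect on the most informative measure would carry no more weight than any other line in the table. What is at stake is the credibility of the neurodevelopment conclusion. The alcohol conclusion has its own biomarker outcome.

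**Working it through.** **The plan's own figures.** Sample size gives 5% significance and 90% power for a difference in alcohol prevalence, with 240 children followed and 30% lost: 240 × (1 − 0.30) = 168, which reproduces. Neither the power nor any other figure there refers to a neurodevelopment score, so there is no planned error rate to reproduce for this aim.

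**Counting the comparisons.** The documents allow two readings.

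| Instrument | One result per instrument and time point | Areas and domains tested separately |
|---|---|---|
| Neurosonography, 28 and 32 weeks | 2 | 2 |
| ASQ-3, 6 and 12 months | 2 | 5 × 2 = 10 |
| IBQ-R, 12 months | 1 | 1 |
| Bayley-III, 18 months | 1 | 3 |
| FASD assessment, 18 months | 1 | 1 |
| Total | 7 | 17 |

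The first reading needs an overall ASQ-3 and Bayley-III score that the plan does not define. The second needs separate testing that the plan does not announce. Sub-measures of the scans or of IBQ-R would add to either total.

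**Chance of at least one false positive.** Assume no true effect and each test at 5%. If the k tests are independent, the chance is 1 − 0.95^k:

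- k = 7: 1 − 0.95^7 = 0.302, with 7 × 0.05 = 0.35 false positives expected.
- k = 17: 1 − 0.95^17 = 0.582, with 17 × 0.05 = 0.85 expected.

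Measures on the same child are likely to be correlated. The documents give no correlations, so the range below is an assumption. It comes from 200,000 simulated sets of equally correlated normal statistics, tested two-sided at 5%.

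| Assumed correlation | 7 comparisons | 17 comparisons |
|---|---|---|
| 0 (formula) | 30% | 58% |
| 0.3 | 27% | 49% |
| 0.5 | 23% | 39% |
| 0.7 | 18% | 27% |
| 0.9 | 11% | 15% |

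A single named endpoint would hold this at 5%, given a test that is valid at 5%.

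**Is each test really at 5%?** The listed tests treat children as independent, although 8 centres were randomised. As an illustration, take 168/8 = 21 children per centre and an assumed intraclass correlation of 0.01. The design effect is 1 + 20 × 0.01 = 1.2. A nominal 5% test then has an error of about 2 × [1 − Φ(1.96/√1.2)] = 2 × [1 − Φ(1.79)], or about 7%. Naming one endpoint is therefore not enough unless its analysis allows for the clusters.

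**What the Bayley-III comparison could detect.** Assume 168 children split evenly, a two-sided 5% test and no clustering. The detectable difference in standard deviations is (1.96 + 0.84) × √(4/168) = 0.43 at 80% power, and (1.96 + 1.28) × √(4/168) = 0.50 at 90%. With the design effect of 1.2, the 80% figure becomes 0.43 × √1.2 = 0.47.

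**The case against.** The best reply is that these are secondary measures. The protocol does not promise a yes-or-no answer on neurodevelopment, no sentence says an isolated significant area will be claimed, and treating several secondary measures as exploratory is legitimate. That would settle the matter if the plan said so. It does not call them exploratory or secondary, and Study design places the neurodevelopment aim beside the alcohol aim.

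Several stronger readings are tempting, and the documents do not support them.

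- *That 17 is a minimum.* It depends on testing every ASQ-3 area and Bayley-III domain separately, which is nowhere stated. The range is 7 to 17 before any scan or IBQ-R sub-measures.
- *That 58% is the expected error.* It is the independence figure for the larger count.
- *That the questionnaires are answered by an unmasked, and so biased, mother.* ASQ-3 and IBQ-R are described as parent-report. The same section names mothers as respondents for the depression scale, so the mother is a likely respondent here but not a stated one. Randomization and intervention says that participants are unaware of the allocation. One may doubt how well that holds for a woman who receives the interviews, but rater bias remains a possibility that the documents neither establish nor give a direction to.

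A fair objection to relying on Bayley-III is that the plan states neither masking of its examiner nor power for that comparison. Both points stand, and the fix has to allow for them.

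**Conclusion.** The concern holds for the neurodevelopment aim. The plan states the aim, spreads it over five instruments, and fixes no endpoint, ranking or multiplicity rule. If every result is tested at 5%, the chance of at least one false positive is about 11% to 30% for 7 comparisons and about 15% to 58% for 17. The lower ends assume a correlation of 0.9 and the upper ends independence. These figures also assume no true effect, equal correlation between measures, and tests valid at 5%; ignoring the clusters would raise the per-test error if the intraclass correlation is positive.

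A reader might infer that the trial's main result is compromised. It is not: the primary outcome is a separate, biomarker-based measure of alcohol intake.

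**What to change.** In Outcomes, name one key secondary neurodevelopment endpoint, the Bayley-III mental score at 18 months, and base the neurodevelopment conclusion on it. It is already planned, is the latest scored developmental test, and is not described as parent-report.

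In Statistical analysis:

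- Compare that score between all randomised arms, with a method that accounts for the 8 clusters and is suited to so few. Say explicitly that children of both arms are included, because Sample size describes the follow-up in terms of prenatally exposed children while Postnatal procedures follows both groups.
- Report the other Bayley-III scales, ASQ-3, IBQ-R, neurosonography and the FASD assessment as supportive, with intervals and no significance claims.
- Label ASQ-3 and IBQ-R as parent-report from families that received the allocated care. Do not label them unmasked, and do not state that the mother is the respondent.
- State whether the Bayley-III examiner is unaware of the arm.

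The change is to wording, with no added visits, tests or participants. It has two costs. An isolated difference on a supportive scale can no longer be claimed as an effect. And because the plan states no power for the Bayley-III comparison, a null result must be read from its interval and not taken as evidence of no effect.

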#### Sample size

Assuming a prevalence of ethanol consumption in our environment of at least 40% in the control group and about 25% (or less) in the intervention group. Thus, about 240 of prenatally exposed children will be followed up in their postnatal period. According to previous experience cohort studies, we may assume a maximum of 30% of loss during their ambulatory control. Regarding this estimate, 168 children will complete their follow up. This sample size can ensure a 90% of potency to detect differences of prevalence between both groups, with a signification of 5%.

Values were corrected regarding number of clusters (n= 8) and intraclass correlation coefficient. Intraclass correlation coefficient was estimated regarding the prevalence of ethanol intake among groups.

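### The 90% power for the prevalence comparison is attached to a postnatal count of exposed children that cannot carry it, and 40% versus 25% does not reproduce it for that count

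*Combined protocol and SAP*

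**What the plan says.** All of the sizing is in the Sample size section of the Combined protocol and SAP. It assumes prevalences of ethanol consumption of "at least 40% in the control group and about 25% (or less) in the intervention group". From these it concludes that "about 240 of prenatally exposed children will be followed up in their postnatal period". A maximum loss of 30% during postnatal follow-up is deducted, so that "168 children will complete their follow up". The next sentence reads "This sample size can ensure a 90% of potency to detect differences of prevalence between both groups", at a 5% significance level. A closing paragraph adds "Values were corrected regarding number of clusters (n= 8) and intraclass correlation coefficient".

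The section does not give the number of women enrolled, whether the counts are total or per arm, the ICC or design effect, or whether the test is one- or two-sided.

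Three other sections bear on the point:

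- **Outcomes** makes the presence of ethanol biomarkers (EtG in maternal hair, PEth in cord blood) the primary outcome.
- **Prenatal procedures** fixes when they are taken: "Samples will be collected at the moment of delivery to obtain to different biomarkers". The same section has AUDIT-C as a second measure of intake: "This questionnaire will be filled during first trimester of pregnancy and also up to 7 days after delivery".
- **Postnatal procedures** describes who is followed: "After both groups (the experimental and control) have delivery, a postnatal follow-up to participants (mothers and children) will be given". It sets no exposure condition, and neither do the eligibility criteria under Participants.

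**The concern.** The power statement and the count it follows concern different things. The power is for a difference between arms in how many women drank. The count is of children already described as exposed. Within such a group the prevalence of exposure is 100% in both arms, so there is nothing to compare.

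The 30% deduction does not fit either. It describes children lost during postnatal follow-up, whereas the primary outcome is measured in samples taken at birth, before any of that loss.

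Two things are at stake. A reader cannot tell what power the trial has for its primary comparison, because the count that should support the 90% is missing or mislabelled. A reader also cannot tell how large the postnatal cohort is meant to be, or whether 240 and 168 refer to all children followed or only to the exposed among them.

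**Working it through.** **Inputs from the Sample size section:** control prevalence p1 = 0.40; intervention prevalence p2 = 0.25; counts 240 and 168; loss 30%; significance 5%; 8 centres.

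**Assumptions where the plan is silent:** 1:1 allocation; equal centre sizes; two-sided test, with one-sided also shown; ICC of 0, 0.005 and 0.01 for illustration.

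**Step 1. The plan's own figures.** 240 × 0.70 = 168, which reproduces. The 90% is checked next.

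**Step 2. Power if the counts mean all children.** With n per arm and pooled variance under the null,

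power = Φ{[|p1 − p2|√n − z√(2p̄(1 − p̄))] / √(p1(1 − p1) + p2(1 − p2))}

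Here p̄ = 0.325, √(2 × 0.325 × 0.675) = 0.6624 and √(0.24 + 0.1875) = 0.6538. z is 1.960 two-sided or 1.645 one-sided.

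- 168 in total, n = 84: (0.15 × 9.165 − 1.2982)/0.6538 = 0.117, power 54.7%.
- 240 per arm: (0.15 × 15.492 − 1.2982)/0.6538 = 1.569, power 94.2%.

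For clustering, n is divided by the design effect 1 + (m − 1) × ICC, where m is the number per centre (total/8).

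| Reading of the count | n per arm | m | Two-sided, ICC 0 | One-sided, ICC 0 | Two-sided, ICC 0.005 | Two-sided, ICC 0.01 |
|---|---|---|---|---|---|---|
| 168 in total | 84 | 21 | 54.7% | 66.9% | 50.8% | 47.4% |
| 240 in total | 120 | 30 | 70.1% | 80.1% | 64.2% | 59.0% |
| 168 per arm | 168 | 42 | 83.8% | 90.4% | 76.5% | 69.8% |
| 240 per arm | 240 | 60 | 94.2% | 97.0% | 87.2% | 79.8% |

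The number per arm for 90% two-sided, before clustering, is [(1.960 × 0.6624 + 1.2816 × 0.6538)/0.15]² = 202.8, so 203. A count of 240 per arm therefore keeps 90% up to a design effect of 240/202.8 = 1.18, which is an ICC of 0.18/59, about 0.003.

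**Step 3. Larger effects.** The prevalences are stated as bounds, so a larger difference is allowed. By the same formula, two-sided and before clustering, 240 in total gives 92.7% at 40% versus 20%. A count of 168 in total gives 81.3% at 40% versus 20% and 92.4% at 50% versus 25%.

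**Step 4. Enrolment if 240 are the exposed children of a larger sample.** At 1:1 the pooled prevalence is (0.40 + 0.25)/2 = 0.325, so 240/0.325 = 738 women, or 369 per arm. About 369 × 0.40 = 148 would be exposed in the control arm and 369 × 0.25 = 92 in the intervention arm. Over every possible allocation split the total lies between 240/0.40 = 600 and 240/0.25 = 960.

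At 738, power is 99.2% before clustering, 95.2% at ICC 0.005 and 88.5% at ICC 0.01. It stays at 90% up to a design effect of 369.2/202.8 = 1.82, which is an ICC of 0.82/91.3, about 0.009.

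**Step 5. Exposed children if 240 are all children.** 120 × 0.40 + 120 × 0.25 = 78, of whom about 55 (78 × 0.70) would remain after 30% loss. Depending on how 240 is read, then, the cohort holds either 240 exposed children or about 78.

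**The case against.** The best defence is that 240 is the expected exposed subset of a larger enrolled sample. The text moves from the two prevalences to the 240 as a consequence, and it then claims a cluster correction. On that reading about 738 women are enrolled and 90% holds over a range of small ICCs. This is a fair reading, and it means that the power statement and the cohort count could both be true. It still requires the power sentence to refer to an enrolment figure that appears nowhere, although the sentence directly follows the 168 children.

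Other routes to 90% before clustering also exist: 240 per arm two-sided, 168 per arm one-sided (90.4%), 240 in total at 40% versus 20%, or 168 in total at 50% versus 25%. Each needs a per-arm count or a one-sided test that the section does not state, or an effect larger than 40% versus 25%. None of them includes the cluster correction that the section says was made.

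The objection also stands on who is followed. A reader might infer that Sample size and Postnatal procedures flatly contradict each other. They need not: Sample size does not say that only exposed children are followed, so 240 could be a count within the wider cohort that Postnatal procedures describes.

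A reader might further infer that the trial will compare arms among exposed children only, which would select on the primary outcome and depart from intention-to-treat. The documents do not support that. No exposed-only analysis is planned, and Statistical analysis divides all analyses by group. Nor would the argument hold in that form if exposure meant first-trimester AUDIT-C rather than delivery biomarkers.

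**Conclusion.** The point holds as a misattached power statement that cannot be reproduced. The 90% does not follow from 168 exposed children, because prevalence cannot vary among them. Nor does it follow from 168 children of any exposure status at 40% versus 25% with a two-sided test: power is 55% if 168 is the total and 84% if it is per arm, before clustering. Without the postnatal loss, which does not apply to the primary outcome, the figures are 70% and 94%, and the 94% falls to 87% at ICC 0.005 and 80% at ICC 0.01.

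It would be tempting to conclude that the trial is underpowered. The documents do not show that, because 90% may hold for an unstated number of enrolled women, such as the 738 or so implied if 240 are exposed children.

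The figures rest on 1:1 allocation, equal centres and illustrative ICCs, none of which the plan gives. The mislabelling of the count depends on none of these.

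**What to change.** In Sample size:

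1. Base the power statement on the number of enrolled women per arm expected to have a delivery biomarker result, without the 30% postnatal loss.
2. Restate the power at 40% versus 25% with the ICC, design effect and sidedness actually used. If the result is below 90%, state the lower figure.
3. Give the postnatal cohort as a separate count. Say whether 240 and 168 are totals or per arm, and whether they count all children or exposed children; if exposed, say by which measure and at what time.
4. Reconcile that count with Postnatal procedures, which follows participants of both arms whatever their exposure.

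If only children with positive delivery biomarkers were to be followed, any comparison of arms among them should be labelled non-randomised.

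The cost is rewording, and possibly a less favourable stated power. No change to recruitment or procedures follows from this point alone.

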### Statistical analysis

Analysis will be conducted by intention-to-treat. Missing data for the main outcome will be handled by complete data analysis because women without an answer on the main outcome will be excluded. All analyses will be divided by groups (control vs experimental group). Continuous data will be assessed for normality using the Kolmogorov-Smirnoff test. Normally distributed variables will be compared among groups using t-test and expressed as mean and standard deviation (SD), while not normally distributed variables will be compared using the Mann-Whitney-U test and expressed as medians and interquartile range (IQR). Quantitative variables will be compared using  $\chi^2$  test and expressed as counts (n) and proportions (%). For categorical variables Fisher exact test or Chi-squared test are used. Regarding demographic data (age, sex, body mass index (BMI), etc.); continuous variables will be presented as mean and SD, or median and IQR, according to their distribution, and categorical variables as percentages (%).

For the main outcome, differences in prevalence of ethanol intake between groups will be analyzed using absolute risk increase defined as the incidence of the outcome in the experimental group minus the incidence in the control group. The absolute risk increase will be depicted in a forest plot. A multivariate logistic regression will be performed to determine the Odds Ratio for ethanol intake adjusting by demographic characteristics. Data will be analyzed using R Core Team (2018). R: A language and environment for statistical computing. R Foundation for Statistical Computing, Vienna, Austria. URL <https://www.R-project.org/> and GraphPad Prism version 8.1.2, GraphPad Software, San Diego, California USA, [www.graphpad.com](http://www.graphpad.com).

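### The plan allows for up to 30% loss in postnatal follow-up but gives no missing-data method for the child outcomes

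*Combined protocol and SAP*

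**What the plan says.** All references are to the Combined protocol and SAP.

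- **Study design** makes the effect on offspring neurodevelopment part of the trial's purpose.
- **Sample size** says that "about 240 of prenatally exposed children will be followed up in their postnatal period", that "we may assume a maximum of 30% of loss during their ambulatory control", and that "168 children will complete their follow up". Loss is given as one overall maximum, not by arm.
- **Postnatal procedures** schedules ASQ-3 ("It will apply at 6 and 12 months of age"), IBQ-R at 12 months, and Bayley-III and a FASD assessment at 18 months, for both groups.
- **Prenatal procedures** schedules sociodemographic data, SCL-90 and AUDIT-C in the first trimester, fetal neurosonography at 28 and 32 weeks, and EtG and PEth at delivery.
- **Statistical analysis** states that "Missing data for the main outcome will be handled by complete data analysis", promises intention-to-treat, and names the t-test, Mann-Whitney, chi-squared and Fisher tests for group comparisons. Logistic regression is reserved for ethanol intake. No mixed model, imputation, weighting, comparison of lost with retained children, or sensitivity analysis is named.

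**The concern.** The one missing-data rule covers the outcome that postnatal loss cannot touch, while the outcomes exposed to a planned loss of up to 30% have no rule. Applied to Bayley-III at 18 months, a two-group test uses only children with a Bayley-III score. A child last seen at 12 months would drop out of that comparison, although ASQ-3 scores, the mother's biomarkers and her baseline questionnaires may all be on file.

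The comparison of returners is unbiased only if loss distorts both arms equally. Families with heavier drinking, poorer mental health or social difficulty may be harder to retain, and their children may score differently. If that process differs between arms, the neurodevelopment answer is distorted and data already scheduled for collection go unused. An intention-to-treat statement does not by itself say how children without a score are to be counted.

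**Working it through.** **1. The plan's own figure.** From Sample size: 240 × (1 − 0.30) = 168, which reproduces exactly. Children lost: 240 − 168 = 72.

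**2. Which outcomes the loss reaches.**

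| Outcome | When | Exposed to postnatal loss | Missing-data rule |
|---|---|---|---|
| EtG, PEth (primary) | delivery | no | complete data |
| ASQ-3 | 6 and 12 months | yes | none |
| IBQ-R | 12 months | yes | none |
| Bayley-III, FASD assessment | 18 months | yes | none |

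**3. Bias formula.** In one arm let L be the share lost and D the mean of retained children minus the mean of lost children, in SD units, with higher scores better. The full-arm mean equals the retained mean − L × D, so the retained mean is too high by L × D. For intervention minus control:

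bias = L(int) × D(int) − L(con) × D(con)

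With the same gap D in both arms this is (L(int) − L(con)) × D.

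**4. Numbers.** The documents give no loss by arm, no D and no SD for any child outcome. All values of L by arm and of D below are assumptions.

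| Loss, control / intervention | D = 0.25 | D = 0.5 | D = 1.0 |
|---|---|---|---|
| 30% / 30% | 0 | 0 | 0 |
| 35% / 25% | −0.025 | −0.05 | −0.10 |
| 40% / 20% | −0.05 | −0.10 | −0.20 |

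The unequal-loss rows run from 0.025 (about 0.03) to 0.20 SD. The sign is negative because the intervention arm is assumed to lose fewer children, so a real benefit would be understated. Reversing the loss rates reverses the sign.

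Equal loss is safe only if the gap is also equal. If loss is selective in the control arm alone, the size is L(con) × D: from 0.30 × 0.25 = 0.075 to 0.40 × 1.0 = 0.40 SD.

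**5. Scale.** With 168 children split 1:1 (assumed; 84 per arm), two-sided 5% and no clustering, the detectable difference at 90% power is (1.960 + 1.282) × √(2/84) = 0.50 SD. Clustering raises it. The common-gap bias in step 4 is smaller than this.

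**The case against.** **The plan never says that child outcomes use returners only.** True. That is an inference from the named tests and from silence. The timing of loss is also not given, so the number of lost children who would have an ASQ-3 score is unknown. But a t-test or Mann-Whitney test on a score can use only children who have it, and nothing else is named for these outcomes. The inference stands.

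**A reader might infer that the bias is as large as the effect the trial seeks.** The documents do not support this. They state no effect, SD or power for any child outcome. The one stated effect ("at least 40% in the control group and about 25% (or less) in the intervention group") concerns maternal consumption, measured by biomarkers at delivery. One could construct an implied child effect of 0.15d, where d is the effect of exposure on the score and 0.15 = 0.40 − 0.25. If the gap D is then set equal to d, the ratio of bias to effect is simply the loss difference divided by 0.15: 0.10/0.15 = 67%, 0.20/0.15 = 133%. That restates the assumed loss difference. Through exposure alone, D = d would need every lost child to be exposed and every retained child unexposed.

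A milder illustration (assumed) has 40% exposed, with 45% of exposed and 20% of unexposed children lost:

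- Overall loss is 0.18 + 0.12 = 0.30.
- The exposed share is 0.18/0.30 = 60% of the lost and 0.22/0.70 = 31% of the retained, so the gap is 0.29d.
- With a 20-point loss difference the bias is 0.20 × 0.286d = 0.057d, or 38% of 0.15d.

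The 0.15d benchmark also fails if only exposed children are followed, which the Sample size wording permits.

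**A reader might also infer that the intervention arm is retained better because its women have extra contact with staff.** Interventions and procedures and the Randomization section place the motivational interview within existing prenatal visits, and Postnatal procedures gives both groups the same follow-up. Uneven loss is a possibility to guard against; the documents do not predict it.

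**Conclusion.** The concern holds as a gap in the analysis plan. Up to 72 of 240 children may be lost, the only missing-data rule covers an outcome measured before that loss, and the tests named for child scores would ignore lost children and their earlier data. If loss or its selectivity differs by arm, the child comparisons are biased.

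The size cannot be stated from the documents. The working range of about 0.03 to 0.20 SD rests on assumed losses of 35%/25% to 40%/20% and an assumed gap of 0.25 to 1.0 SD common to both arms. The bias is zero if loss and gap are both equal. It hides benefit if the intervention arm loses fewer children, and it can be larger if selection occurs in one arm only. The primary biomarker outcome is untouched by this loss. The change is inexpensive and should be made before child outcomes are examined by arm.

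**What to change.** In Statistical analysis:

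- Analyse ASQ-3 at 6 and 12 months in one mixed model with a centre (cluster) effect, so that a child seen once still contributes. The centre term is needed because 8 centres were randomised.
- Analyse Bayley-III after multiple imputation by arm, using ASQ-3 at both ages, EtG and PEth, AUDIT-C, SCL-90, sociodemographic data and centre, with an analysis model that accounts for clustering. State whether IBQ-R is handled in the same way.
- Tabulate retention by arm and by biomarker status.
- Add one sensitivity analysis that shifts the imputed values of lost children downward by an amount stated in advance.
- Keep the comparison of completers as supportive.

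In Sample size, state whether the 240 followed children are only those prenatally exposed or all children. The answer determines what the between-arm child comparison means and how informative retention by biomarker status can be.

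The cost is SAP wording and additional analysis work; no new data are needed. The downside is reliance on a missing-at-random assumption, which the shifted analysis probes but cannot remove. Inverse-probability weighting is a reasonable alternative to imputation if the team prefers it. What matters is that one method is fixed in advance.
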